10.1.3. Smoking Diary Compliance

Subjects will record their cigarette consumption in a daily diary for 7 consecutive days during the screening period, and each day during the 25-day treatment period (i.e. on Day 1 through Day 25, inclusive). For each period (screening, treatment), compliance with diary reporting requirements will be derived as:

$$[(\# \text{ diary days entered by subject}) / (\# \text{ diary days expected for subject})] * 100.$$

The number of diary days expected is 7 days for the screening period and 25 days for the treatment period. The number of diary days and compliance will be summarized for each period by treatment arm. Compliance will be summarized both as a continuous variable and as a categorical variable (<80%, 80-<90%, 90-<100%, 100%).

Other elements of protocol-compliance are described in [Section 9.2](#) (study drug compliance) and [Section 9.3](#) (behavioral support compliance).

10.2. Analyses of Other Efficacy Endpoints

The other efficacy objectives are stated in [Section 3.2](#). The other efficacy endpoints are defined in [Section 4.1.2](#). The results for each endpoint will be displayed graphically by treatment arm. Side-by-side bar charts will be used to display categorical endpoints, Kaplan-Meier figures will be used for time-to-event endpoints. For binary endpoints, forest plots will be used to display 95% CIs for the odds ratio.

The other efficacy analyses will be conducted using subjects in the All Randomized Analysis Set described in [Section 6.4](#).

For each of the other efficacy endpoints identified below, 4 within-schedule comparisons of cytosine vs placebo will be performed:

1. 1.5 mg Cytisine – Commercial Schedule vs Placebo – Commercial Schedule
2. 3.0 mg Cytisine – Commercial Schedule vs Placebo – Commercial Schedule
3. 1.5 mg Cytisine – tid Schedule vs Placebo – tid Schedule

4. 3.0 mg Cytisine – tid Schedule vs Placebo – tid Schedule

The statistical analyses that will be performed for the other efficacy endpoints are described below.

10.2.1. Abstinance from Week 5 to Week 8

Abstinance from Week 5 to Week 8 is a binary (success, failure) endpoint. For each of the comparisons listed above, the two treatment arms will be compared in terms of the proportion of subjects classified as a success. Following is template SAS code for doing each of the statistical comparisons where s is the stratification factor (BMI, 3 levels), x is the treatment arm (2 levels, each comparison), and y is the efficacy endpoint (success vs failure).

```
proc freq data=data;  
  exact fisher or comor eqor;  
  table s*x*y / nopercnt nocol;  
run;
```

The effect size estimate of each comparison will be based on the common odds ratio estimate using exact computations for stratified 2x2 frequency tables.

Homogeneity of odds ratios will be assessed using Zelen's Exact Test. If there is evidence of odds ratio heterogeneity across the strata ($p\text{-value} \leq 0.10$) then the analysis will be performed separately for each level of the stratification factor and stratum-specific estimates of the odds ratios and CIs for those odds ratios will be reported.

10.2.2. Sensitivity Analyses for Abstinance from Week 5 to Week 8

The following sensitivity analyses will be performed for the Abstinance from Week 5 to Week 8 endpoint by 

- The placebo treatment arms (Placebo – Commercial Schedule, Placebo – tid Schedule) will be compared. If the proportion of subjects classified as a success is similar for the two placebo arms then each of the cytisine treatment arms will be compared to the pooled placebo arms.

All other sensitivity analyses for the Abstinance from Week 5 to Week 8 endpoint will be conducted by an independent statistician (). These analyses will include exploratory analyses to identify effect modifiers. The variables that will be evaluated as effect modifiers are identified [Section 10.1.2](#). The relationship between treatment arm and the proportion of subjects with abstinance will be evaluated within stratum defined by the effect modifier. For each stratum, the number (%) of subjects within each stratum with abstinance will be reported for each treatment arm. Odds ratios (1.5 mg cytisine vs. placebo, 3.0 mg cytisine vs. placebo) and their 95% CIs will also be reported. Forest plots will be used to display the stratum-specific 95% CIs.

A tipping point analysis will be performed.¹

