2. STUDY DESCRIPTION

2.1. Study Design

This Phase 2b study is a six-arm, multicenter, randomized, double-blind, placebo-controlled, and parallel-design trial of the safety and efficacy of cytisine in adult cigarette smokers who are willing to set a quit date that is 5-7 days after being randomized on the study. A total of 250 subjects are planned to be randomized at the ratio 2:1 to cytisine treatment and the respective placebo treatment as designated by the protocol defined schedule (i.e. the commercial titrated schedule vs the simplified three times daily (tid) schedule) for 25 days. Subjects will be stratified at randomization based on BMI class (18.5 to <25 kg/m²; 25 to <30 kg/m²; 30 to <35 kg/m²) as defined in the protocol. The six treatment arms will be:

Figure 1: Study Design Overview

The study will be comprised of a pre-study screen, followed by twenty-five (25) days of study treatment, an end-of-treatment visit at Week 4 (Day 27 ± 2 days), and weekly post-treatment follow up visits from Week 5 to Week 8 post-randomization.

Blinding

- The study will be double-blinded to dose (1.5 mg cytisine, 3.0 mg cytisine, placebo) but not to the administration schedule (commercial titration schedule, simplified tid schedule).
- Sponsor and contract research personnel responsible for collecting, monitoring and analyzing the study data will also be blinded to dose but not to administration schedule.
- In order to blind the study treatment dose, all subjects will take 2 tablets at every scheduled dosing. Subjects randomly assigned to Arm A or Arm D will take one 1.5 mg cytisine tablet and one placebo tablet at each dosing. Arm B or Arm E subjects will take two 1.5 mg cytisine tablets at each dosing. Arm C and Arm F subjects will receive two placebo tablets at each daily scheduled dosing to correspond to cytisine dosing.

Randomization

- Eligible subjects will be randomized 2:1 in a blinded manner to either Arm A or Arm B vs Arm C (2:1 randomization) or Arm D or Arm E vs Arm F (2:1 randomization)

- Subjects will be stratified at randomization by BMI class (18.5 to <25 kg/m²; 25 to <30 kg/m²; 30 to <35 kg/m²).
- Unique subject number and randomization code will be assigned to each study subject
- Parallel group design

Multicenter Trial

- This study will be conducted at multiple sites across the US

Type of Comparison

- Superiority in favor of cytisine

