2.3. Study Population

Approximately 250 subjects who are daily cigarette smokers intending to make a quit attempt during the study will be enrolled at multiple study sites within the US. Based on the planned 2:1 (cytisine:placebo) randomization, it is expected that 200 subjects will be randomized to receive

cytisine (50 subjects at each cytisine treatment arm) and 50 subjects will be randomized to receive placebo (25 subjects per treatment schedule).

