3.5. Determination of Sample Size

The sample size was computed based on data from a previous Phase 1/2 trial and for achieving narrow confidence intervals (CI) for the primary comparison estimates in this trial.

The trial size was based on projected realization of the effect size estimate for the primary outcome based on data from a Phase 1/2 study in adult smokers. The primary outcome standard deviation from this study was found to be approximately 17. Based on this standard deviation, the estimated between-arm differences in the primary comparisons can be estimated with a 95% CI that is ± 8.3 .

The trial size will not have sensitivity for a dichotomous outcome (e.g. smoking cessation as one of the other efficacy outcomes), other than for possibly large differences. For example, if the control arm outcome is 12% (3/25 defined as successes), then the experimental arm will have a two-sided 95% CI for the probability difference that excludes zero when the success probability is 36% (8/50) or more (computation based on exact CI).

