10.2.3. Initial Quit Rates

The initial quit rate endpoint is binary (success, failure) defined at Week 4 (Day 27 EOT). For each comparison (see [Section 10.2](#)), the treatment arms will be compared in terms of the proportion of subjects classified as a success ([Section 4.1.2](#)). The effect size estimate of each comparison will be based on the common odds ratio estimate using exact computations for stratified 2x2 frequency tables.

If there is evidence of odds ratio heterogeneity across the strata (p-value for Zelen's Exact Test ≤ 0.10) then the analysis will be performed separately for each level of the stratification factor and stratum-specific estimates of the odds ratios and their 95% CIs will be reported.

10.2.4. 7-day Point Prevalence

The 7-day point prevalence endpoints are binary (success, failure) endpoints defined at each of the following visits: Week 5, Week 6, Week 7 and Week 8.

For each comparison (see [Section 10.2](#)), the treatment arms will be compared in terms of the proportion of subjects classified as a success ([Section 4.1.2](#)). The effect size estimate of each comparison will be based on the common odds ratio estimate using exact computations for stratified 2x2 frequency tables.

If there is evidence of odds ratio heterogeneity across the strata (p-value for Zelen's Exact Test ≤ 0.10) then the analysis will be performed separately for each level of the stratification factor and stratum-specific estimates of the odds ratios and their CIs will be reported.

10.2.5. Time to Failure to Maintain Abstinence Through Week 8

Time to failure to maintain abstinence through Week 8 ([Section 4.1.2](#)) will be evaluated for the subgroup of subjects who were classified as a success on the initial quit rate endpoint. Time to failure (days) will be calculated for individual subjects as described in [Section 4.1.2](#). Subjects who are still abstinent at Week 8 will have time to failure censored at the date of the Week 8 visit.

Time to failure will be summarized by treatment arm; the minimum, maximum, median and 95% confidence interval for the median time to failure reported by the LIFETEST procedure will be reported. Two Kaplan-Meier figures of treatment arm by time to failure will be produced, one figure for each schedule (commercial, tid).

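### The binary analyses should not switch from the common odds ratio to separate BMI-class analyses on a homogeneity pre-test at p ≤ 0.10

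*SAP*

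**What the plan says.** For Week 5–8 abstinence, SAP 10.2.1 names one effect measure over the three BMI classes: "The effect size estimate of each comparison will be based on the common odds ratio estimate using exact computations for stratified 2x2 frequency tables". It then adds a condition. If Zelen's exact test suggests that the odds ratios differ between strata, with a cut-off of 0.10, "then the analysis will be performed separately for each level of the stratification factor", and stratum odds ratios with confidence intervals are reported.

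Sections 10.2.3 (initial quit rate) and 10.2.4 (7-day point prevalence at Weeks 5, 6, 7 and 8) repeat the rule. In 10.2.3 the trigger is "p-value for Zelen's Exact Test ≤ 0.10" and the consequence is "then the analysis will be performed separately for each level of the stratification factor and stratum-specific estimates".

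None of the three sections says whether the common odds ratio remains the main result once the trigger is met. None says what to report when a stratum has a zero cell. SAP 6.5 lists Week 5–8 abstinence as a key endpoint, and protocol 5 and 7.3.2 name it as the planned Phase 3 primary endpoint. SAP 6.1 gives estimation as the purpose of the trial and sets no significance level.

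**The concern.** The form of the reported estimate depends on a test run on the same data. Each comparison has 50 active and 25 placebo subjects, so the fallback analysis has about eight placebo subjects in each BMI class. Followed literally, the rule replaces one estimate that uses all 75 subjects with three estimates of about 25 subjects each, some of which may not be finite.

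The stake is estimation, not type I error. For a comparison that switches by chance, the reader would be pointed to BMI-class results that reflect noise. Effect sizes would also be reported in different forms across arms and visits for no substantive reason.

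**Working it through.** **The plan's own figures.** The documents give no figure for how the pre-test behaves. The nearest is the binary example in SAP 3.5: "if the control arm outcome is 12% (3/25 defined as successes", against an active rate printed as 36% with the count 8/50. These disagree: 8/50 = 16%, and 36% is 18/50. Fisher's exact test against 3/25 gives p = 0.032 for 18/50, 0.054 for 17/50 and 0.74 for 8/50, so the percentage looks right and the count a misprint. Both 16% and 36% were used below.

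**Inputs**
- 50 active and 25 placebo subjects per comparison (SAP 2.3). Missing outcomes count as failures (SAP 4.1.2), so these numbers do not shrink.
- Three BMI strata (SAP 2.1). Their sizes are not stated. *Assumption:* equal thirds, 17/17/16 active and 8/8/9 placebo (50/3 = 16.7; 25/3 = 8.3). An unequal split, 12/20/18 and 6/10/9, was also tried.
- Placebo rate 12% from SAP 3.5. *Assumption:* 20% to 50% as the range for other endpoints, for which no rate is given.
- Number of pre-tests: 6 binary endpoints × 4 comparisons = 24, of which 4 concern Week 5–8 abstinence.

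**Method.** Zelen's test was computed from its conditional distribution, with all stratum margins and the total number of active successes fixed. For each setting, 40,000 trials were simulated with the same success rates in every stratum, so every firing is a chance firing.

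**Results, equal split**

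| Placebo / active rate | Rule fires | Given firing: at least one of three stratum odds ratios infinite or undefined | Given firing: share of single stratum odds ratios infinite or undefined |
|---|---|---|---|
| 12% / 12% | 5.1% | 91.7% | 42.1% |
| 12% / 16% | 5.6% | 91.8% | 42.3% |
| 12% / 36% | 5.5% | 92.0% | 43.2% |
| 20% / 36% | 7.6% | 75.8% | 30.5% |
| 30% / 50% | 8.6% | 46.5% | 16.5% |
| 40% / 60% | 8.7% | 21.8% | 7.4% |
| 50% / 50% | 8.9% | 6.5% | 2.2% |

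The unequal split gave 6.0%, 92.1% and 42.5% at 12%/36%, and 9.1%, 47.2% and 16.9% at 30%/50%. Nearly all the non-finite estimates are infinite. Undefined ones (0/0) are at most about 2% of single stratum estimates.

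**Expected chance switches** (placebo rates 12% to 40%)
- Week 5–8 abstinence: 4 × 0.051 = 0.20 to 4 × 0.087 = 0.35.
- All binary endpoints: 24 × 0.051 = 1.2 to 24 × 0.087 = 2.1.
- At least one of the four comparisons of a single endpoint, allowing for the shared placebo arms (15,000 trials per setting): 18–19% at 12% placebo and 26% at 30%.

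**The estimate that would be replaced.** The common odds ratio was finite in 100% of the firings in those shared-placebo simulations. This must be so. If the common estimate is at its limit, only one table fits the fixed margins and Zelen's p is 1, so the rule cannot fire.

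**Finite stratum results say little.** For an illustrative 6/17 against 1/8, the exact 95% CI for the odds ratio is 0.32 to 200. For 6/17 against 0/8 it is 0.62 to infinity.

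**The case against.** The strongest reply is that nothing is lost. The sentence that bases the effect size on the common odds ratio carries no condition. The template SAS code requests the common odds ratio and the homogeneity test in the same run. The conditional sentence adds stratum estimates without saying that the common one is dropped. The table list shows one abstinence table per schedule, and the shells that might settle the matter are redacted. SAP 10 always presents counts and percentages by arm. For Week 5–8 abstinence, SAP 10.2.2 already plans stratum odds ratios for the effect modifiers listed in 10.1.2, which include BMI. No formal testing is planned, and SAP 3.5 already warns that binary outcomes have little sensitivity.

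Much of this stands, and it rules out three stronger readings that a reader might infer.

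- *The comparison would be left with no usable effect size, or Phase 3 could not be sized.* Not supported. The common odds ratio is still computed, arm-level rates are always shown, and an infinite stratum odds ratio still has one finite exact limit.
- *Most stratum estimates would be infinite or undefined.* Not supported. Fewer than half of single stratum estimates are, even at 12% placebo. What is usual at 12–20% is that at least one of the three is.
- *Sparse zero cells cause the false firings.* Not supported. Firing is rarest where the data are sparsest (about 5% at 12% placebo, nearly 9% at 40–50%). At 12%, a stratum with no placebo success already occurs in 1 − (1 − 0.88⁸)² × (1 − 0.88⁹) = 72% of trials, so the figure of about 90% after firing is that background rate, moderately raised.

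The reply does not remove the ambiguity. An instruction to perform the analysis separately by stratum is naturally read as a replacement, and no text says otherwise.

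**Conclusion.** The point holds as a matter of what is reported and relied on. The SAP contains a data-driven switch, repeated for all six binary endpoints, and does not protect the common odds ratio once it fires.

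Under a truly common odds ratio the rule fires in about 5–9% of comparisons. When it does, at least one BMI-class odds ratio is non-finite in about 90% of cases at 12% placebo, about 76% at 20% and about 46% at 30%. For a single stratum estimate the figures are about 41–44%, 31% and 16%. The estimate displaced is finite.

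These sizes rest on roughly equal BMI classes and on the placebo rate. The unequal split tried hardly changed them, but above 30% placebo the non-finite problem fades quickly. For the key endpoint alone, the expected number of chance switches is well below one. This is an inexpensive improvement to an estimation plan, not a flaw that invalidates it.

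**What to change.** In SAP 10.2.1, 10.2.3 and 10.2.4, delete the sentence that makes the analysis depend on Zelen's test. State that the exact BMI-stratified common odds ratio with its 95% CI is always the reported effect estimate. Show counts by BMI class, stratum odds ratios where they can be estimated, and the Zelen p-value as descriptive support. This matches the primary endpoint, where SAP 10.1.2 places the BMI-interaction follow-up under sensitivity analyses.

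The cost is SAP wording only. The downside is that a real BMI interaction would be described and not made the main analysis. Little is given up, because the pre-test is a weak detector at this size. With true stratum odds ratios of 1, 4 and 4 it fires in only 17% (12% placebo) to 28% (30% placebo) of trials, and even with 1, 4 and 16 in only 42–56%.

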10.2.3. Initial Quit Rates

The initial quit rate endpoint is binary (success, failure) defined at Week 4 (Day 27 EOT). For each comparison (see [Section 10.2](#)), the treatment arms will be compared in terms of the proportion of subjects classified as a success ([Section 4.1.2](#)). The effect size estimate of each comparison will be based on the common odds ratio estimate using exact computations for stratified 2x2 frequency tables.

If there is evidence of odds ratio heterogeneity across the strata (p-value for Zelen's Exact Test ≤ 0.10) then the analysis will be performed separately for each level of the stratification factor and stratum-specific estimates of the odds ratios and their 95% CIs will be reported.

10.2.4. 7-day Point Prevalence

The 7-day point prevalence endpoints are binary (success, failure) endpoints defined at each of the following visits: Week 5, Week 6, Week 7 and Week 8.

For each comparison (see [Section 10.2](#)), the treatment arms will be compared in terms of the proportion of subjects classified as a success ([Section 4.1.2](#)). The effect size estimate of each comparison will be based on the common odds ratio estimate using exact computations for stratified 2x2 frequency tables.

If there is evidence of odds ratio heterogeneity across the strata (p-value for Zelen's Exact Test ≤ 0.10) then the analysis will be performed separately for each level of the stratification factor and stratum-specific estimates of the odds ratios and their CIs will be reported.

10.2.5. Time to Failure to Maintain Abstinence Through Week 8

Time to failure to maintain abstinence through Week 8 ([Section 4.1.2](#)) will be evaluated for the subgroup of subjects who were classified as a success on the initial quit rate endpoint. Time to failure (days) will be calculated for individual subjects as described in [Section 4.1.2](#). Subjects who are still abstinent at Week 8 will have time to failure censored at the date of the Week 8 visit.

Time to failure will be summarized by treatment arm; the minimum, maximum, median and 95% confidence interval for the median time to failure reported by the LIFETEST procedure will be reported. Two Kaplan-Meier figures of treatment arm by time to failure will be produced, one figure for each schedule (commercial, tid).

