The second Phase 3 trial (Cytisine As a Smoking Cessation Aid, or CASCAID⁶ trial) was conducted by the Health Research Council of New Zealand and was an open-label trial that randomized 1,310 adult daily smokers. Subjects were randomized to receive either cytisine by the commercial 25-day titration schedule or vouchers for low-cost combination NRT (patch plus gum or lozenges) for 8 weeks. Both treatment groups were offered low-intensity telephone behavioral support during trial treatment. The primary outcome measure was continuous self-reported abstinence from smoking one month after a quit date. The RR for continuous one-month abstinence was 1.3 for cytisine (40% cytisine arm compared to 31% in the NRT arm; $P<0.001$). A secondary outcome included the RR for continuous six-month abstinence which was 1.4 for cytisine (22% cytisine arm compared to 15% in the NRT arm; $P=0.002$). Cytisine was generally

well tolerated, although self-reported adverse events were higher in the cytisine arm compared with the NRT arm. The most frequent adverse events were nausea and vomiting and sleep disorders. Overall, 53% of subjects randomized to receive cytisine were in compliance with the treatment schedule (had taken 80 or more of the required 100 tablets). Subjects in the NRT group showed 67% compliance (using NRT at both 1 week and 1 month). The results of the CASCAID trial, which were published in the *New England Journal of Medicine* in December 2014, showed that cytisine was superior to NRT for smoking cessation and, specifically, that cytisine was 1.43 times more likely than nicotine patches with gum or lozenges to help participants stop smoking and remain non-smokers for six months.⁶

Both studies are described in more detail within the Investigator's Brochure.

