6.2. Other Efficacy Objectives

Each of the following will include comparisons for 1.5 mg or 3.0 mg doses versus placebo when given as the commercial 25-day titration schedule and for the tid treatment schedule as well as comparisons between the commercial 25-day titration versus tid treatment schedules).

1. Assess the probability of abstinence from Week 5 to Week 8 post-randomization in subjects randomized to cytisine as compared to subjects randomized to placebo.
2. To compare cytisine and placebo arms on initial quit rates during study treatment, at Week 4 (End of Treatment) and on 7-day point prevalence abstinence at Week 5, Week 6, Week 7, and Week 8.
3. Among subjects abstinent at Week 4, compare time to failure to maintain abstinence through Week 8 between arms.
4. To explore potential relationships between subject-reported outcomes (e.g. anxiety, withdrawal symptoms, depression, tobacco craving, alcohol use) with the reduction in cigarette smoking during the study Treatment Period, as well as smoking cessation outcomes at Week 4 (End of Treatment) and from Week 5 to Week 8 post-randomization.
5. To explore a potential correlation for subject's nicotine metabolite ratio (NMR) with the reduction in cigarette smoking and smoking cessation outcomes.

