3.2. Other Efficacy Objective(s)

Each of the following will include comparisons for 1.5 mg or 3.0 mg doses versus placebo when given as the commercial 25-day titration schedule and for the tid treatment schedule (as well as comparisons between the commercial 25-day titration versus tid treatment schedules). The other efficacy objectives are:

1. Assess the probability of abstinence from Week 5 to Week 8 post-randomization in subjects randomized to cytisine as compared to subjects randomized to placebo.
2. To compare cytisine and placebo arms on initial quit rates during study treatment, at Week 4 (End of Treatment) and on 7-day point prevalence abstinence at Week 5, Week 6, Week 7, and Week 8.
3. Among subjects abstinent at Week 4 (End of Treatment), compare time to failure to maintain abstinence through Week 8 between arms.
4. To explore potential relationships between subject-reported outcomes (e.g. anxiety, withdrawal symptoms, depression, tobacco craving, alcohol use) with the reduction in cigarette smoking during the study treatment period, as well as smoking cessation outcomes at Week 4 (End of Treatment) and from Week 5 to Week 8 post-randomization.
5. To explore a potential correlation for subject's nicotine metabolite ratio (NMR) with the reduction in cigarette smoking and smoking cessation outcomes.

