4.1.2. Other Efficacy Endpoints

The endpoints associated with the other efficacy objectives are:

Abstinence from Week 5 to Week 8 is a binary endpoint (success, failure). Success is defined for a subject as having reported smoking abstinence (no cigarettes since the last clinic visit and over the past 7 days) at each clinic assessment from Week 5 to Week 8 with biochemical verification at each assessment. Biochemical verification will be defined by a CO concentration in exhaled breath of less than 10 ppm. Subjects will be allowed only 1 missed visit (smoking status and/or biochemical verification status unknown) between Week 5 and Week 8 (i.e. one of Week 6 or Week 7 visits only) for analysis of the abstinence from Week 5 to Week 8 endpoint.

Any outcome other than success will be regarded as a failure. There are therefore two types of failure for subjects: (1) subjects with adequate data that they were smoking at any time from Week 5 to Week 8 (either by the subject's self-report of smoking or CO \geq 10 ppm) and (2) subjects having insufficient data to be determined as a success for abstinence from Week 5 to

Week 8 endpoint (e.g., subjects lost to follow-up, missing the Week 5 and/or Week 8 clinic visit, or missing both the Week 6 and Week 7 visits).

All subjects will have a realization of this endpoint, thereby enabling analyses that follow the intent-to-treat (ITT) principle without imputation.

Initial quit rate is a binary endpoint (success, failure) at Week 4 (Day 27 EOT). Success is defined for a subject as having reported smoking zero cigarettes in the subject diary at Day 25, with biochemical verification by an expired-air CO reading <10 ppm at the Day 27 EOT clinic visit. Any other outcome will be regarded as a failure. This endpoint is defined at the End of Treatment visit so that subjects have approximately a 2½-week grace period after the Day 5-7 quit date. All subjects will have a realization for this endpoint, thereby enabling analyses that follow the ITT principle without imputation.

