7-day point prevalence is a binary endpoint (success, failure) at each of the following visits: Week 5, Week 6, Week 7 and Week 8. At each visit, success is defined for a subject as having reported not smoking any cigarettes over the past 7 days with biochemical verification by an expired-air CO reading <10 ppm. Any other outcome will be regarded as a failure. All subjects will have a realization of this endpoint, thereby enabling analyses that follow the ITT principle without imputation.

Time to failure to maintain abstinence through Week 8 will be evaluated for the subgroup of subjects who were classified as a success for the initial quit rate endpoint (see previous definition). Time to failure to maintain abstinence (days) will be calculated as end date of abstinence minus start date of abstinence + 1. The start date of abstinence will be defined as the date of the Week 4 (Day 27 EOT) visit. The end date of abstinence will be defined as the earliest date that the subject was known to have resumed smoking. Specifically:

- At a visit, if a subject reported not smoking in the past 7 days but has smoked since the last visit (either by the subject's self-report or $CO \geq 10$ ppm), the end date of abstinence will be the date of that last visit.
- At a visit, if a subject reported not smoking since the last visit but has smoked in the past 7 days (either by the subject's self-report or $CO \geq 10$ ppm), the end date of abstinence will be defined as the date of the visit minus 7 days.
- Subjects who have not resumed smoking at the final (Week 8) visit will have end date of abstinence censored at the date of the Week 8 visit.

Relationship between Outcome Variables and Smoking Reduction and Cessation

Endpoints: The relationships between subject-reported outcomes (e.g. anxiety, depression, withdrawal symptoms, tobacco craving, alcohol use) and the following smoking efficacy endpoints will be evaluated:

- The primary efficacy endpoint, which measures reduction in smoking during the study treatment period.
- Initial quit rate, which evaluates smoking cessation at Week 4 (Day 27/EOT).

- Abstinence from Week 5 to Week 8.

It is expected that the relationship between each of these efficacy variables and the following subject-reported outcome variables will be evaluated for this objective:

- Change during the treatment period, in self-reported number of cigarettes smoked over the previous 24 hours.

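### SAP 10.2.5 plans no between-arm estimate for time to failure, and the medians it plans will probably not be reached in the cytisine arms

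*SAP*

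**What the plan says.** Objective 3 in Protocol 6.2 reads: "Among subjects abstinent at Week 4, compare time to failure to maintain abstinence through Week 8 between arms". SAP 3.2 repeats it. SAP 10.2 then commits, for each of the other efficacy endpoints, that "4 within-schedule comparisons of cytosine vs placebo will be performed" (the spelling is the SAP's).

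For Week 5 to 8 abstinence, initial quit rate and 7-day point prevalence (SAP 10.2.1, 10.2.3, 10.2.4), the SAP names the effect estimate: a common odds ratio, stratified by BMI class, with exact computation. For time to failure, SAP 10.2.5 says by arm that "the minimum, maximum, median and 95% confidence interval for the median time to failure reported by the LIFETEST procedure will be reported", and adds one Kaplan-Meier figure per schedule. It names no survival proportion at a fixed time, no hazard ratio, no difference and no test.

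Under SAP 4.1.2 the analysis covers only subjects who succeeded on the initial quit endpoint, defined as "having reported smoking zero cigarettes in the subject diary at Day 25, with biochemical verification by an expired-air CO reading <10 ppm" at the end-of-treatment (EOT) visit. The clock starts at that visit. Subjects who have not resumed smoking are censored at the Week 8 visit.

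**The concern.** A Kaplan-Meier median exists only if about half of an arm's Week 4 quitters relapse before follow-up ends. If fewer do, the median is reported as not reached. The other two statistics do not fill the gap. The minimum is one subject's time. In any arm with a continuing abstainer, the maximum is essentially a Week 8 visit date and reflects the visit windows.

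Objective 3 would then have curves but no planned number that compares arms. SAP 6.1 gives the goal of the study as effect-size estimates to inform later trials. Relapse between Week 4 and Week 8 bears on the intended Phase 3 endpoint, abstinence from Week 5 to Week 8.

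**Working it through.** The plan gives no expected figure for this endpoint, so there is none to reproduce.

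**1. Length of follow-up.** EOT is Day 27 (±2) and Week 8 is Day 56 (±3). Elapsed time is 56 − 27 = 29 days, ranging from 53 − 29 = 24 to 59 − 25 = 34. The SAP formula adds one day: 30, range 25 to 35.

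**2. Relapse, derived from the protocol.** For the open-label cytisine-versus-NRT trial, Protocol 2 gives one-month abstinence of 40% and 31%, and six-month abstinence of "22% cytisine arm compared to 15% in the NRT arm". Retention over the five months is 22/40 = 0.55 (cytisine) and 15/31 = 0.484 (NRT). On cytisine, even the five-month horizon did not reach a median.

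**3. Scaling to 29 days.** With r the five-month retention and k a Weibull shape (assumed), S = r^[((29/30.4)/5)^k], where (29/30.4)/5 = 0.191.

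| Shape k | Cytisine S | NRT S |
|---|---|---|
| 1.0 (constant hazard) | 0.89 | 0.87 |
| 0.5 | 0.77 | 0.73 |
| 0.3 (strongly front-loaded) | 0.70 | 0.64 |
| all five months' relapse within 4 weeks | 0.55 | 0.484 |

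**4. Chance that the median is reached.** P = P[Binomial(n, 1 − S) ≥ n/2], with no losses. Exactly half counts as reached, which if anything favours the plan. The number of Week 4 quitters, n, is not in the documents; I assume 8 to 25 per cytisine arm.

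| Relapse by Week 8 | n = 8 | n = 20 | n = 25 |
|---|---|---|---|
| 11% | 0.7% | <0.1% | <0.1% |
| 23% | 9% | 0.8% | 0.2% |
| 27% | 14% | 2% | 0.7% |
| 35% | 29% | 12% | 6% |
| 45% | 52% | 41% | 31% |

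At n = 20 the chance is 0.3% at 20% relapse and 5% at 30%.

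**5. Confidence interval of the median.** In simulation (4,000 runs per setting, weekly event times, log-log limits, n from 5 to 25, S from 0.484 to 0.89), the upper limit was reached in at most 7% of runs. The lower limit is often estimable: at S = 0.77, in 88% of runs at n = 8, 50% at n = 20 and 20% at n = 25.

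**6. Placebo.** With an assumed 3 to 8 quitters, the same formula gives 3% (n = 7) to 18% (n = 4) at 20% relapse, and 39% (n = 7) to 61% (n = 4) at 45%. The placebo-controlled trial in Protocol 2 had 3.5% six-month abstinence on placebo. If 12% to 31% had quit at Week 4 (assumed), 29-day S is 0.66 to 0.79 at constant hazard and 0.27 to 0.47 at shape 0.3. The placebo median could therefore fall either way.

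**7. Precision of a fixed-time proportion.** The half-width is 1.96 × √[S(1 − S)/n]. At S = 0.77 this is ±18 points for n = 20 and ±29 for n = 8. For a difference between arms of 20 and 8 with S = 0.77 in both, 1.96 × √[0.1771 × (1/20 + 1/8)] = ±35 points.

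**The case against.** The strongest reply is that the section gives more than a bare median, and that little depends on it.

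- A reader might infer that objective 3 gets no usable number. The documents do not support that. The CI of the median and the Kaplan-Meier figures are both planned, a lower limit may be estimable, and retention can be read from the curves. What is missing is a planned between-arm estimate.
- A reader might infer that the protocol states a relapse rate for this period. It does not. The 55% is derived from subjects continuously abstinent for a month, whereas entry here needs only zero cigarettes on Day 25 plus CO below 10 ppm. Relapse may be faster, and 45% is not a strict ceiling: the NRT figure packed into 4 weeks gives 52%, where the chance at n = 20 is 64%.
- A reader might infer that no arm will reach its median. Step 6 shows that this cannot be said of placebo. Even so, a reached placebo median against an unreached cytisine median gives no difference.
- Losses are not modelled. Protocol 13 counts unknown smoking status as failure in the cessation analyses; SAP 10.2.5 is silent. If 20% were lost and counted as failures, S = 0.77 would become 0.77 × 0.8 = 0.62.
- The shells for Tables 14.2.8.1 and 14.2.8.2 are redacted, so further statistics there cannot be ruled out. The text of 10.2.5 itself is complete.
- Time to failure is not among the key endpoints in SAP 6.5. Week 5 to 8 abstinence is, and it already has an exact odds ratio.

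These points limit the claim and lower the stakes. They do not supply the comparison that SAP 10.2 promises.

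**Conclusion.** The concern holds in a limited form. SAP 10.2.5 names no between-arm estimate, although objective 3 and SAP 10.2 call for comparisons. The per-arm medians it does name will probably not be reached in the cytisine arms: at 20 Week 4 quitters, the chance is under 1% at relapse of up to 23%, 5% at 30% and 41% at 45%.

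This rests on assumed numbers of Week 4 quitters, retention borrowed from a trial with a stricter starting cohort, an assumed shape for the relapse curve, and no losses. It weakens with very few quitters and fast relapse together: at n = 8 and 45% relapse, reaching the median is close to a coin toss. Because the endpoint is not a key one, this is a low-cost improvement to the SAP and does not threaten the trial's main conclusions.

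**What to change.** In SAP 10.2.5:

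- Keep the median and its CI where the median is reached.
- Add the Kaplan-Meier proportion still abstinent at one prespecified day, with a 95% CI, for each arm. Choose a day at or before the earliest in-window Week 8 censoring time, about 24 days after the EOT visit (25 on the SAP's scale), so that subjects still abstinent and seen within the windows are not censored before it.
- Report the difference in that proportion for the four within-schedule comparisons, with 95% CIs, labelled descriptive.
- State how Week 4 quitters lost before Week 8 enter the estimate.
- Carry the additions into Tables 14.2.8.1 and 14.2.8.2 if they are not already there.

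The proportions come from the same LIFETEST run, the differences follow from them, and no new data are needed. The costs are that a time point must be named in advance and that the intervals will be wide (step 7). A hazard ratio or log-rank test would also answer the objective, but with roughly 5 to 8 events per comparison its power would be only about 15% to 19% for hazard ratios of 0.36 to 0.44, so it too would be descriptive.
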